Comparison in the mean change achieved in the allopurinol treatment minus placebo phase between African Americans and other races/ethnicities will be performed initially using a t-test for independent samples. If differences are identified in the distribution of covariates, then the analysis will be completed with analysis of variance.

Assessing change in serum urate on change in hsCRP, FMD, and blood pressure

For this aim, the independent variable is change in serum urate and the outcome is change in hsCRP, FMD, and BP. First, participant factors associated with a significant change in serum urate will be identified using unadjusted age, race/ethnicity, and gender adjusted linear regression models. The correlation between change in serum urate with change in hsCRP, FMD, and SBP and DBP will be calculated using Spearman correlation coefficients. Using linear regression models, the association between changes in serum urate with changes in levels of each outcome, separately, will be determined. Models will include initial adjustment for age, gender, and race/ethnicity with subsequent models adjusted for other potential confounders (e.g. estimated glomerular filtration rate). In analyzing the association of change in serum urate on change in BP, we will additionally adjust for hsCRP and FMD, individually and together. The reduction in the association (i.e. beta coefficient) between change in serum urate and change in BP from before to after adjustment for these variables will provide insight into the degree that these mechanisms mediate the relation between ULT and BP reduction.

With 56 African Americans and 56 other races/ethnicities, we will be able to detect a difference in the increase of FMD of 1.48% for allopurinol versus placebo in African Americans compared to other participants.

The primary analyses will be on an intent-to-treat basis. All statistical analysis will be performed using SAS statistical software (SAS, Cary, NC) by analysts masked to randomization assignment. All study related information will be entered into a study database. This database will be maintained on a secure computer with access limited to study personnel only.

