Research information that identifies subjects will be shared with the UAB Institutional Review Board (IRB) and others who are responsible for ensuring compliance with laws and regulations related to research, including the U.S. Food and Drug Administration (FDA); and the Office for Humans Research Protections (OHRP). The results of this study may be published in scientific journals or presented at medical meetings, but study participants identity will remain confidential.

Calculation of sample size.

Power and sample size for aim 1c

In a prior study, a standard deviation of 8.5 mmHg for mean SBP by 24-hour ABPM in young and normotensive patients studied over 4 months has been reported.⁸¹ Using this standard deviation and similar assumptions as outlined above (alpha of 0.05 and a correlation of 10% between pairs of SBP measurements for each subject), we will have 90% statistical power to detect a 3.7 mmHg difference in the change in SBP with allopurinol treatment versus placebo. An intra-individual variation (standard deviation) of the difference between two values on a same patient in DBP by ABPM of 6.3 mmHg has been reported previously by an international consensus conference.⁸² Using this standard deviation and 90% statistical power, we will be able to detect a change in DBP of 2.0 mmHg for treatment with allopurinol versus placebo. For comparing African Americans versus participants of other race/ethnicities (assuming 46 participants in each group), we will have 90% statistical power to detect a difference in SBP and DBP of 5.8 mmHg and 4.3 mmHg, respectively.

Power and sample size for aim 1b.

The standard deviation of the difference between two values obtained in the same patient has been reported to be 2.5%.⁸⁰ With an alpha of 0.05, statistical power of 0.90, assuming a 10% within-period correlation of change in FMD and the sample size of 93 individuals calculated for hsCRP, we will be able to detect a change in FMD of 1.15% between allopurinol treatment and placebo. With 46 African Americans and 46 other races/ethnicities, we will be able to detect a difference in the increase of FMD of 1.48% for allopurinol versus placebo in African Americans compared to other participants.

Power and sample size for aim 1a.

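### The detectable race differences for SBP, FMD and hsCRP conflict with the plan's own overall figures; on the SDs behind those figures, power is about 54% to 71%, not 90%

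*Combined protocol and SAP*

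**What the plan says.** All of this is in section H of the protocol.

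- **Analysis.** Under the heading on differential effects by race/ethnicity, the plan specifies an independent-samples t-test: "Comparison in the mean change achieved in the allopurinol treatment minus placebo phase between African Americans and other races/ethnicities". Overall, Aims 1a to 1c compare the change in the active phase with the change in the placebo phase by paired t-test.
- **SBP.** The calculation (headed aim 1c) takes an SD of 8.5 mmHg and "a correlation of 10% between pairs of SBP measurements for each subject". It concludes that "we will have 90% statistical power to detect a 3.7 mmHg difference in the change in SBP with allopurinol treatment versus placebo". By race, with 46 per group, "we will have 90% statistical power to detect a difference in SBP and DBP of 5.8 mmHg and 4.3 mmHg, respectively".
- **DBP.** The SD of the difference between two values in one patient is 6.3 mmHg. "Using this standard deviation and 90% statistical power, we will be able to detect a change in DBP of 2.0 mmHg".
- **FMD.** With an SD of 2.5%, a 10% correlation, 90% power and 93 people, "we will be able to detect a change in FMD of 1.15% between allopurinol treatment and placebo". By race, "With 46 African Americans and 46 other races/ethnicities, we will be able to detect a difference in the increase of FMD of 1.48" percent. Earlier in section H the same figure appears with a different group size: "With 56 African Americans and 56 other races/ethnicities, we will be able to detect a difference in the increase of FMD of 1.48" percent. Neither race sentence states a power; 0.90 comes from the sentence before the 46-per-group version.
- **hsCRP.** With an SD of 0.52, a 10% correlation and 90% power, 93 complete participants are needed to detect 0.25 log mg/L. By race, with 46 per group and 90% power, the printed difference is 32 log mg/L, illustrated by 10 and 42.

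No separate SD is given for any race comparison.

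**The concern.** The overall and race analyses use the same person-level variable. If its SD is common to both, the two detectable differences are tied together by sample size alone. Splitting about 93 people into two groups of 46 roughly doubles the detectable difference. Three of the four outcomes fall well short of doubling, so each printed pair assumes two different SDs for one quantity.

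Hypotheses 2, 4 and 6 are the race comparisons, three of the seven hypotheses, and equal recruitment and stratified randomization serve them. A reader who trusts the 90% could take a null race result as good evidence against a 5.8 mmHg or 1.48% difference, when the plan's own assumptions give much weaker sensitivity.

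**Working it through.** **Method.** Two-sided alpha 0.05, 90% power, noncentral t. The plan prints n = 93 for FMD and hsCRP; I assume the same n for blood pressure. Let S be the SD of the per-person allopurinol-minus-placebo difference.

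- Overall (paired t, n = 93): detectable difference = 0.3397 × S
- Race (two-sample t, 46 per group): detectable difference = 0.6832 × S
- Expected ratio: 0.6832 / 0.3397 = 2.01. The large-sample form agrees: √(2/46) / √(1/93) = 2.01.

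**Step 1: reproduce the overall figures.** With correlation 0.10, S = s × √(2 × (1 − 0.10)) = s × √1.8.

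- FMD: 2.5 × √1.8 = 3.354, giving 1.14 (stated 1.15).
- hsCRP: 0.52 × √1.8 = 0.698 gives 0.237 and would need n = 84. Only 0.52 × √2 = 0.735 returns 0.25 with n = 93.
- SBP: 8.5 × √1.8 = 11.40, giving 3.87 (stated 3.7; power at 3.7 is 87%).
- DBP: 6.3 unscaled, giving 2.14 (stated 2.0; power at 2.0 is 86%).

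Unscaled SDs would give overall figures of 2.89 (SBP), 0.85 (FMD) and 0.18 (hsCRP), so they are not what produced 3.7, 1.15 and 0.25.

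**Step 2: ratios and implied SDs.** Overall figures are divided by 0.3397, race figures by 0.6832.

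| Outcome | Race / overall | Ratio (expect 2.01) | S from overall | S from race |
|---|---|---|---|---|
| SBP | 5.8 / 3.7 | 1.57 | 10.89 | 8.49 |
| FMD | 1.48 / 1.15 | 1.29 | 3.39 | 2.17 |
| hsCRP (32 read as 0.32) | 0.32 / 0.25 | 1.28 | 0.736 | 0.468 |
| DBP | 4.3 / 2.0 | 2.15 | 5.89 | 6.29 |

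**Step 3: race comparison on the SDs behind the overall figures, 46 per group.** The lower S for SBP and the higher S for FMD and hsCRP are back-solved from the printed overall figure; the other value is s × √1.8.

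| Outcome | S | Difference at 90% power | Power at printed difference |
|---|---|---|---|
| SBP, 5.8 | 10.89 / 11.40 | 7.44 / 7.79 | 71.4% / 67.5% |
| FMD, 1.48 | 3.354 / 3.385 | 2.29 / 2.31 | 55.3% / 54.5% |
| hsCRP, 0.32 | 0.698 / 0.736 | 0.477 / 0.503 | 58.6% / 54.1% |
| DBP, 4.3 | 6.3 | 4.30 | 89.9% |

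On the back-solved SDs, 90% power at the printed race differences needs 76 (SBP), 111 (FMD) and 113 (hsCRP) per group.

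**Step 4: the same comparison with unscaled SDs.**

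- SBP, S = 8.5: detectable 5.81, power 89.9%. So 5.8 reproduces, but the overall figure becomes 2.89.
- FMD, S = 2.5: power 80.2% at 1.48.
- hsCRP, S = 0.52: power 83.1% at 0.32.

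**Step 5: the 56 + 56 FMD sentence.** With S = 3.354 to 3.385 and 56 per group, the detectable difference is 2.07 to 2.09 and power at 1.48 is 63–64%. At equal power and SD, 1.48% cannot be right for both 46 and 56 per group.

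**The case against.** **SBP.** The strongest point is that 5.8 does follow from the only SBP SD the plan prints, while 3.7 follows only roughly from 8.5 with the stated correlation. This stands to the extent that the arithmetic proves the pair irreconcilable rather than proving 5.8 to be the wrong member. The 67–71% is conditional on the overall figure. But the unscaled reading sets aside the 10% correlation that the text applies to 8.5. The overall SBP sample size is also unprinted: 8.5 × √2 with n = 112 gives 3.71, but race power at 5.8 is then only 63% (46 per group) or 72% (56 per group).

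**FMD and DBP are handled differently.** Both SDs are described as differences between two values in one patient, yet only FMD is scaled here. The reason is empirical: only the scaled 2.5 reproduces 1.15, only the unscaled 6.3 reproduces 4.3, and no correlation is given for DBP. If 6.3 were scaled by √1.8, DBP power at 4.3 would be 67%. Accepting 4.3 therefore depends on 6.3 being the SD of the treatment difference.

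**The SDs may be understated.** The tested quantity is a difference of two changes. If 8.5 were the SD of a single measurement and r = 0.10 applied at both steps, S would be 8.5 × 1.8 = 15.3, the race difference 10.5 mmHg and power at 5.8 about 44%. The replacement values are thus one reading, which is why the SD should be declared first.

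**Unstated power and missing decimals.** FMD's 1.48 matches an undeclared 80% power with SD 2.5, and hsCRP's 0.32 matches 56 per group with SD 0.52 (89.8%). These may explain where the figures came from, but both contradict the overall figures, and the hsCRP one also contradicts the stated 46 per group. Reading 32 as 0.32 is an assumption, and a decimal point could have been lost in text extraction. Beside an SD of 0.52 and an effect of 0.25, no other reading is plausible.

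**Conclusion.** The concern holds. For SBP, FMD and hsCRP, the overall and race detectable differences cannot both be right at 90% power with 46 per group. On the SDs behind the overall figures, power at the printed race differences is about 67–71%, 55% and 54–59%. For FMD and hsCRP even the unscaled printed SDs reach only 80% and 83%. For SBP, 5.8 can be kept only by giving up 3.7. DBP 4.3 is consistent with its printed SD; the overall DBP figure of 2.0 is slightly optimistic.

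This rests on a common SD for the overall and race tests, n = 93 overall, two-sided alpha 0.05, 90% power carried over to the FMD race sentence, and 32 read as 0.32. The error concerns the stated sensitivity for Hypotheses 2, 4 and 6. It does not affect the planned sample size, which comes from the overall hsCRP comparison, and should be corrected as wrong as written.

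**What to change.** 1. For each outcome, state one SD for the within-person allopurinol-minus-placebo difference, how it was obtained, and the correlation used.
2. Recompute the overall and race figures from that SD. Print either the corrected race differences or the actual power at the printed ones. On the present assumptions the differences are about 7.4–7.8 mmHg (SBP), 2.3% (FMD) and 0.48–0.50 log mg/L (hsCRP).
3. If 8.5 is meant as the SD of the SBP treatment difference, keep 5.8 and correct the overall 3.7 to about 2.9.
4. Keep DBP 4.3, stating that 6.3 is the SD of the treatment difference.
5. Remove or recompute the 56 + 56 FMD sentence, and state the power in the FMD race sentence.
6. Correct 32, 10 and 42 log mg/L to 0.32, 0.10 and 0.42, or to the recomputed values.

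The cost is wording in section H. Sample size and conduct do not change; the FMD and hsCRP race figures become less favourable, as does SBP unless 8.5 is declared the SD of the difference.

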Pill count			X	X	X	X		X	X	X	X
Adverse events reporting			X	X	X	X		X	X	X	
Physical exam	X		X**			X**		X**			X**
BP screening	X		X			X		X			X
Focused medical history	X										
Updated medical history			X			X		X			X
Randomization			X								
24-hr ABPM			X			X		X			X
FMD			X			X		X			X
Blood sample	X		X			X		X			X
CBC	X		X			X		X			X

Project 2: The Effects of Urate Lowering Therapy on Inflammation, Endothelial Function, and Blood Pressure (NIAMS: CORT)

Liver tests*	X		X		X		X		X	
Pregnancy test [†]	X		X		X		X		X	
Serum creatinine	X		X		X		X		X	
Serum urate	X		X		X		X		X	
hsCRP			X		X		X		X	
Cotinine	X		X		X		X		X	
Serum banking [§]			X		X		X		X	
Contact check in				X	X		2X		X	X

PE-physical examination, BP-blood pressure, ABPM-ambulatory blood pressure monitoring, FMD-flow mediated dilation of the brachial artery, hsCRP-highly sensitive C-reactive protein

*Liver tests are alanine aminotransferase, aspartate aminotransferase, and alkaline phosphatase. At screening only, a bilirubin test was performed.

** Physical exams will be conducted following screening visit only in cases where rash has been reported

[†]Only in women

^{††}Revised timeline corresponded to reduction in washout phase from 4 to 2 weeks for male participants and female participants depending on menstrual cycle.

[§]Sera and whole blood (for DNA extraction) will be stored.

Visit 1:

- Informed Consent
- Blood pressure
- Physical Exam
- Focused medical history
- Blood sample
- Urine sample
- CBC
- Liver tests-Liver tests are alanine aminotransferase, aspartate aminotransferase, and alkaline phosphatase
- Serum creatinine
- Serum urate
- Pregnancy test[†]
- Cotinine test
- Dispense placebo run-in if all qualifications are met

Visit 2 will occur 2 weeks following the screening procedures, signing of the consent form, and 2 week long (±3 days) placebo run-in period in the UAB Hypertension Clinic. For pre-menopausal women, run-in was timed so the end of the run-in will coincide with the onset of their menses and no later than day 7 of the next cycle for standardized measurements of FMD, thus run-in was typically of a 28-day duration. ⁷⁵ Compliance with placebo run-in will be assessed through pill count. Before and after each intervention phase, the markers for

the study primary (serum urate, hsCRP, endothelial function as measured by FMD) and secondary outcomes (ambulatory BP monitoring) will be collected. Other data will be collected as needed for safety monitoring.

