As allopurinol is classified as FDA class C during pregnancy pregnant women will not be allowed in the study. Women with recent deliveries or third trimester pregnancy losses in the previous 3 months will be excluded because of unpredictable effects on FMD. A special question about the use of azathioprine will be included, since this can have a severe interaction with allopurinol.⁷⁸ Participants with serious medical conditions that in the investigator's judgment pose an unacceptable risk for exposure to a fixed dose of allopurinol (e.g. advanced heart failure, advanced liver disease or cirrhosis) will also be excluded.

H. Data collection and Statistical Analyses (see also Data Analysis plan)

Measures of central tendency (sample mean, sample media) and dispersion (sample variance, sample standard deviation) will be calculated for all outcome variables (e.g., hsCRP, endothelial function, and BP on ABPM) and covariates (e.g. age, race, etc.). For outcome variables, distributional properties will be evaluated using histograms and normal probability plots. When the assumption of normality is questionable, outcome

variable transformations will be examined to determine if the transformed variables approximate a normal distribution. will be transformed to achieve normality. Of the main study measures, we anticipate the distribution of hsCRP to be highly skewed. Consistent with prior studies, we will log transform hsCRP values for analysis. Possible outlying or inconsistent values will be detected and explored

Aim 1a: ULT and change in BP. The change in the average weighted 24-hour mean SBP and DBP will be compared among participants during the active treatment and placebo phases by paired t-test analysis.

Aim 1b: ULT and change in FMD. The change in the FMD will be compared among participants during the active treatment and placebo phases by paired t-test analysis.

Aim 1c: ULT and change in hsCRP. For each participant, we will first calculate the change in log transformed hsCRP from the beginning to the end of each crossover phase. The lack of an effect for the treatment sequence on the relative treatment responses will be confirmed using a treatment by sequence interaction term. Next, the within-participant change in hsCRP will be compared during the allopurinol treatment and placebo phases by paired t-test analysis.

Assessing differential treatment effects by race/ethnicity

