As mentioned above, it is anticipated that the distribution for hsCRP will be skewed, and thus, we will log transform hsCRP. The sample size for the study is based on having 90% statistical power, assuming a two-tailed alpha error of 5% and a within person correlation of log transformed hsCRP between measurements of 10%. The intra-person standard deviation for log transformed hsCRP has been reported to be 0.52 log mg/L on serial measurements extending into a one year period.⁷⁹ To detect a difference in log transformed hsCRP of 0.25 (log mg/L) will require a sample size of 93 participants with complete hsCRP measurements (i.e., from baseline and closeout visits for each of the study phases). This is equivalent to a net reduction of hsCRP of 25% (e.g., from 2 mg/L to 1.5 mg/L or from 1 mg/L to 0.75 mg/L). This difference was chosen as it represents approximately half of one standard deviation in log-transformed hsCRP and is a meaningful decline to be observed over a four week period. Although we expect minimal loss to follow-up, we have taken the conservative step of increasing the sample size to account for 20% of participants not having complete data. Thus, we will recruit and randomize 112 participants for the proposed trial. For comparing differences in the net reduction in hsCRP for African Americans in comparison to other races/ethnicities, with 46 African Americans and 46 other races/ethnicities, we will have 90% statistical power to detect a differential reduction in log transformed hsCRP of 32 log mg/L (e.g., a 10 log mg/L reduction in whites and a 42 log mg/L reduction in African Americans).

Table 4. Statistical Power for Aim 2			
Proportion of Outcome Variance Explained by Control Variables	Incremental increases in R² due to the addition of change in serum urate in the presence of the control variables		
	.05	.075	.10
.10	.64	.82	.92
.20	.69	.87	.95
.30	.75	.91	.97

Power and sample size for aim 2

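### hsCRP sizing: the plan does not say whether 0.52 is the SD of one log value or of a within-phase change, so the stated 90% power is conditional; the hsCRP and FMD race figures do not hold at 46 per group on either reading

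*Combined protocol and SAP*

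**What the plan says.** **Planned test.** For hsCRP (section H, Aim 1c), "we will first calculate the change in log transformed hsCRP from the beginning to the end of each crossover phase"; then "the within-participant change in hsCRP will be compared during the allopurinol treatment and placebo phases by paired t-test analysis".

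**Sample size.** This is under section H, Calculation of sample size. The hsCRP paragraph carries the heading for aim 1a, although hsCRP is aim 1c elsewhere. It assumes two-sided alpha 0.05, 90% power and "a within person correlation of log transformed hsCRP between measurements of 10" percent. On the SD: "The intra-person standard deviation for log transformed hsCRP has been reported to be 0.52 log mg/L on serial measurements", over up to one year. A difference of 0.25 "will require a sample size of 93 participants with complete hsCRP measurements (i.e., from baseline and closeout visits for each of the study phases"). The 0.25 is justified as "approximately half of one standard deviation in log-transformed hsCRP". Allowing for 20% incomplete data, 112 are to be randomised.

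**Role of hsCRP.** Section F (Visit 2) says the markers for "the study primary (serum urate, hsCRP, endothelial function as measured by FMD) and secondary outcomes (ambulatory BP monitoring) will be collected".

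**FMD.** The adjacent calculation does label its SD: "The standard deviation of the difference between two values obtained in the same patient has been reported to be 2.5" percent. With a 10% correlation between changes and the 93 taken from hsCRP, it gives a detectable difference of 1.15%.

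**Race comparisons.** With 46 per group and 90% power, the hsCRP paragraph claims a differential printed as 32 log mg/L. FMD is given as 1.48% at 46 per group in the sample-size section, and as 1.48% at 56 per group in the section on assessing associations with serum urate.

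**The concern.** Subtracting a baseline in each phase adds the noise of two more measurements. If those are only weakly correlated with the end-of-phase values, the variance of the contrast roughly doubles. A sample size that allows for one differencing step is therefore right for the planned test only if the SD entered was already that of a change. The hsCRP paragraph does not say so, although the FMD and DBP paragraphs do say it for theirs.

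This matters because hsCRP sets the size of the trial, is listed among the primary markers, and supplies the 93 reused for FMD. The race comparisons (Hypotheses 4 and 6) rest on the same SDs but do not appear to use them in the same way.

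**Working it through.** **Inputs from section H:** difference 0.25; SD 0.52; correlation 0.10; two-sided alpha 0.05; 90% power; 93 completers; race groups of 46; FMD SD 2.5%. Paired power is from the noncentral t with n - 1 degrees of freedom and noncentrality (0.25/SD_net) x sqrt(n). Race comparisons use the two-sample t-test.

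**1. Reproducing 93.** SD_net = 0.52 x sqrt(2(1 - rho)).
- rho = 0: SD_net = 0.735, n = 93, power at 93 = 90.0%.
- rho = 0.10, as stated: SD_net = 0.698, n = 84, power at 93 = 92.8%.

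So 93 is reproduced with the stated correlation left out. The SD of 0.735 fits two situations equally: the planned test with 0.52 as a change SD, or one value per phase with 0.52 as a single-value SD. The figure 93 cannot tell them apart.

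**2. The planned test if 0.52 is the SD of one value.** Net change = (end - start on allopurinol) - (end - start on placebo).

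| Correlation | SD_net | Power at 93 | Completers for 90% |
|---|---|---|---|
| 0 | 0.52 x 2 = 1.040 | 63.1% | 184 |
| 0.10 among all four values | 0.52 x sqrt(3.6) = 0.987 | 67.7% | 166 |
| 0.10 at both differencing steps | 0.52 x 1.8 = 0.936 | 72.2% | 150 |

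With larger within-phase correlation (between-phase correlations equal, so they cancel), SD_net = 2 x 0.52 x sqrt(1 - rho). Power at 93 is 73% at 0.2, 78% at 0.3, 84% at 0.4 and 90% at 0.5.

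**3. FMD overall.** SD_net = 2.5 x sqrt(1.8) = 3.354 at n = 93 gives a detectable difference of 1.14%, against 1.15% stated. Here a phase-change SD with 10% correlation between changes closely reproduces the plan.

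**4. hsCRP race comparison, 46 per group, differential read as 0.32.**

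| Net-change SD | Power for 0.32 | Detectable at 90% |
|---|---|---|
| 0.52 used directly | 83% | 0.355 |
| 0.735 (the SD that yields 93) | 54% | 0.50 |
| 0.936 to 1.04 (single-value reading) | 37% to 31% | 0.64 to 0.71 |

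An SD of 0.52 used directly gives 0.32 only at 56 per group. The documents do not show which input was used.

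**5. FMD race comparison.** An SD of 2.5% used directly gives 1.55% at 56 per group and 1.71% at 46, so 1.48% matches neither. On the basis that reproduces 1.15% overall (SD_net 3.354), the figure at 46 per group is about 2.29%.

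**6. Baseline-adjusted alternative (simulation, n = 93).** End-of-phase log hsCRP was adjusted for the phase baselines.
- Single-value reading (correlation 0, 0.10 among all four values, 0.10 at both steps): 89.6%, 92.6% and 92.7%, against 62.9%, 67.9% and 72.1% for change scores.
- Change-SD reading, within-phase correlation 0.3 to 0.9: 91-98%, against 89-93%.
- Type I error of both tests: 4.9-5.1%.

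**7. Minor.** 112 x 0.8 = 89.6 completers; at 89 and SD_net 0.735, power is 88.7% against 90.0%. exp(-0.25) = 0.779, a 22% reduction if natural logs are meant, against the stated 25%.

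**The case against.** The strongest reply is that nothing is miscalculated in the overall hsCRP comparison: 93 and 90% reproduce, and the plan's own 10% correlation does slightly better. The context also supports the change-SD reading. The adjacent FMD calculation enters a phase-change SD and correlates the two changes, and the 93 is defined by baseline and closeout values in each phase. This stands as evidence of how the number may have been entered. It does not show what the cited 0.52 measured, and FMD matches at 10% correlation whereas hsCRP matches only at zero. The hsCRP wording points the other way: 0.25 is called half an SD of log hsCRP itself, and no difference label is attached.

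Second, 0.52 comes from measurements spread over up to a year, while each phase lasts four weeks. Values four weeks apart may correlate above 10%, which would raise the 63-72%. That is fair, and is why the sensitivity to 0.5 is shown. The 10% is nonetheless the plan's own figure.

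Third, the attrition and percentage points are small: 93 x 1.2 = 111.6 is a common inflation and costs about one point of power. They are treated as minor here.

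A reader might infer that the trial is underpowered for hsCRP, or that the planned t-test is invalid. The documents support neither inference. The low power is conditional on one reading of 0.52, the paired t-test keeps its type I error, and a null result can still be read from its confidence interval.

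**Conclusion.** The concern holds as a gap in specification for the overall hsCRP comparison, and as an inconsistency of figures for the race comparisons.

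- **Overall hsCRP.** The claim of 90% power depends on an SD basis that the plan does not state. It is met if 0.52 is a change SD. If 0.52 is the SD of one value, the shortfall at the plan's 0-10% correlation is about 18 to 27 percentage points. The cited source is not available here, so which reading is right stays open.
- **Race, hsCRP.** 90% power at 46 per group is not reached on any SD basis considered. This rests on reading the printed 32 as 0.32; as printed it is not a usable value.
- **Race, FMD.** One detectable difference is given for two different group sizes, and the stated SD reproduces it at neither.

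This should be fixed. Confidence is medium, because the size of the overall hsCRP effect turns on the unstated meaning of 0.52.

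**What to change.** 1. Recompute the hsCRP and FMD race figures at 46 per group, using the same net-change SD as the overall comparison (about 0.50 log units on the basis that gives 93, and about 2.29% for FMD). Correct the printed 32, and remove the duplicate FMD statement at 56 per group or reconcile it.
2. While analysts are still masked, replace the raw change-score paired t-test for hsCRP with an analysis of end-of-phase log hsCRP adjusted for the two phase baselines. If unblinding has already happened, report this as a sensitivity analysis. The SAP should also say whether the race and serum-urate analyses stay on change scores.
3. State whether 0.52 is the SD of one log value or of a within-phase change, and which pairs of the four values the 10% describes. If change scores are kept and 0.52 is a single-value SD, restate hsCRP power as about 63-72%, with the correlation sensitivity.
4. Minor: state that 112 with 20% incomplete leaves about 89-90 completers, name the log base, and describe 0.25 as a 22% reduction if it is natural.

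The cost is SAP wording and a few lines of code. The hsCRP values are already scheduled, and no more participants are needed.

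### The hsCRP design target of 0.25 log units is not a 25% reduction: it is 22% on the natural log and 44% on log10, and the plan does not state the base

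*Combined protocol and SAP*

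**What the plan says.** The hsCRP calculation is in section H, Calculation of sample size, in the paragraph headed Power and sample size for aim 1a (section B lists hsCRP as aim 1c). It starts from "The sample size for the study is based on having 90% statistical power", a two-sided 5% alpha and a 10% within-person correlation. The variability input is given as "The intra-person standard deviation for log transformed hsCRP has been reported to be 0.52 log mg/L on serial measurements". The result is: "To detect a difference in log transformed hsCRP of 0.25 (log mg/L) will require a sample size of 93 participants".

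The target is then put into clinical units: "This is equivalent to a net reduction of hsCRP of 25% (e.g., from 2 mg/L to 1.5 mg/L", with 1 to 0.75 mg/L as a second example. It is justified as "approximately half of one standard deviation in log-transformed hsCRP and is a meaningful decline to be observed over a four week period".

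The analysis text for aim 1c in section H compares within-participant change in log hsCRP between the allopurinol and placebo phases by paired t-test. Neither that text nor the sample-size paragraph says which logarithm is meant.

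**The concern.** A difference in logs is a ratio on the original scale, so 0.25 log units has to be back-transformed before it is called a percentage. Here 0.25 seems to have been read straight across as 25%. Both worked examples (2 to 1.5 and 1 to 0.75 mg/L) are exact 25% reductions, so this is not rounding.

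The statement matters because hsCRP is one of the primary outcomes named in section F (Visit 2 text), and its calculation sets the trial size. The FMD power paragraph for aim 1b also reuses the 93. Anyone reading section H would conclude that the trial has 90% power for a 25% reduction.

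The percentage is also the only clue to the log base, and it matches neither usual base. The same paragraph gives subgroup reductions of 32, 10 and 42 log mg/L, which cannot be literal log values. That is a further reason to state the scale.

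**Working it through.** **Inputs, all from the aim 1a paragraph of section H:** two-sided alpha 0.05; power 0.90; SD 0.52 log mg/L; correlation 0.10; difference 0.25 log mg/L; stated N 93. The log base is not given, so both usual bases are carried through.

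**1. Reproduce the 93.** For a paired comparison, N = (z₀.₉₇₅ + z₀.₉₀)² × SD_diff² / δ², with (1.960 + 1.282)² = 10.507.

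- Correlation left out: SD_diff = 0.52 × √2 = 0.735. N = 10.507 × 0.5408 / 0.0625 = 90.9, so 91 by the normal approximation and **93** by the noncentral t. This matches the plan; power at 93 is 90.0%.
- Stated 10% correlation used: SD_diff = 0.52 × √(2 × 0.9) = 0.698. N = 81.8, so 82 (normal) or 84 (t). This does not match 93; power at 93 is 92.8%.

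The plan's 93 is therefore the N for δ = 0.25 with the stated correlation omitted. Both SDs are shown below.

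**2. Convert 0.25 to a percentage.**

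- Natural log: 1 − exp(−0.25) = 1 − 0.779 = 22.1%, that is 2 to 1.56 mg/L or 1 to 0.78 mg/L.
- Log10: 1 − 10^(−0.25) = 1 − 0.562 = 43.8%, that is 2 to 1.12 mg/L.

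**3. Convert 25% to log units.**

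- Natural log: ln(2/1.5) = 0.288, which is 0.288/0.25 = 1.15 times the target used.
- Log10: log10(2/1.5) = 0.125, half the target used.

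**4. N and power for a true 25% reduction (paired t-test).** The log10 rows assume that 0.25 and 0.52 are both in log10 units.

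| Base | δ for 25% | SD_diff | N for 90% power | Power with 93 |
|---|---|---|---|---|
| Natural | 0.288 | 0.735 (correlation omitted) | 71 | 96.2% |
| Natural | 0.288 | 0.698 (correlation 0.10) | 64 | 97.6% |
| Log10 | 0.125 | 0.735 (correlation omitted) | 366 | 36.8% |
| Log10 | 0.125 | 0.698 (correlation 0.10) | 330 | 40.1% |

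In no row do 93 completers, 90% power and a 25% reduction go together.

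**The case against.** The best defence is that this is a loose gloss with no effect on the trial. N was derived from 0.25 and not from the percentage, and 0.25 was chosen first as about half an SD (0.25/0.52 = 0.48). Reading a small natural-log difference as a percentage is common shorthand, and here it is out by about 3 percentage points in the safe direction. Much of this stands: on the natural log, N, enrolment, the test and the type I error are untouched. It does not rescue the sentence, which claims equivalence and backs it with two exact 25% examples. Nor can the safe direction be taken for granted, because the base is not documented. Natural log is the likelier reading only because 22% lies nearer to 25% than 44% does.

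A reader might infer more than the documents support:

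- **That there are two targets**, a clinical 25% and an analysed 0.25. The paragraph sets one target and translates it wrongly; it defines no separate clinical threshold.
- **That an observed reduction of 22–24% would meet one benchmark and fail another**, or that the result should be judged against 22%. The plan has no such rule. The paired t-test is against zero, and with n = 93 and SD 0.735 an observed difference of about 1.986 × 0.735/√93 = 0.151 natural-log units, roughly 14%, already reaches p = 0.05.
- **That the trial is underpowered.** This would follow only on the log10 reading, which nothing in the documents establishes.

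**Conclusion.** The point holds as a wrong design statement for a named primary outcome. That 0.25 log units is not 25% is certain on either usual base, and nothing elsewhere in the documents corrects it. The size of the error depends on the base: about 3 percentage points on the natural log (22.1% against 25%) and about 19 on log10 (43.8% against 25%).

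Whether the error is harmless is also conditional. On the natural log it is conservative, with about 96–98% power for a true 25% reduction. If both inputs were log10 values, that power would be about 37–40%. These powers take over the plan's SD of 0.52 as an SD of single measurements, the reading that reproduces 93 when the correlation is left out. Whether that SD suits a comparison of changes between phases is a separate question.

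**What to change.** State the log base used for hsCRP, both in the aim 1c analysis text and in the sample-size paragraph, and make the percentage and examples agree with 0.25.

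- If natural log: replace 25% by about 22% and give the examples as 2 to 1.56 mg/L or 1 to 0.78 mg/L. N stays at 93.
- If 25% is the intended target on the natural log: state the difference as 0.288 and give the power at 93, about 96% with SD 0.735 or about 98% with the stated 10% correlation.
- If log10: describe 0.25 as about a 44% reduction and state that power for 25% at 93 is about 37–40%.

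Say also whether the 10% correlation was used, since 93 reproduces only without it. On the natural log the cost is a sentence of text, with no change to enrolment or to the analysis.
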